2a: Self-reported cardiovascular (CV) health. In the cohort described in Aim 1, CV health will be assessed by the American Heart Association's Life's Simple 7 (LS7) scores. H2a: Pre/post changes in LS7 scores will show a greater positive change among intervention clients compared with controls.

2b: Nutritional quality of food selected. We will perform pre/post client cart assessments to measure the nutritional quality of foods selected by clients at their food pantry visit, as measured by HEI scores, in a repeated cross-sectional study H2b: On average, HEI scores among clients at intervention food pantries will be higher after the intervention compared with controls.

Aim 3: To evaluate the impact of the intervention on the nutritional quality of food offered at food pantries, measured by a pre/post Food Assortment Scoring Tool (FAST). H3: Pre/post FAST scores will show a greater positive change among intervention food pantries (n = 8) compared with controls (n = 8).

Aim 4: To measure implementation of policies and practices that promote a nutrition-focused hunger relief network, as assessed by pre/post surveys and key informant interviews with hunger relief agency staff.

Exploratory aim: To evaluate the cultural appropriateness of food shelf foods and services as measured by: (1) the availability of culturally-specific food, and (2) client satisfaction assessed by pre/post surveys.

Outcomes:

Primary Endpoint/Event/Outcome: The primary outcome is change in overall diet quality scores among clients, as measured by the USDA's Healthy Eating Index (HEI). A cohort of clients will take two 24 hour recalls at each time point to measure overall dietary quality.

Secondary Endpoint(s)/Event(s)/Outcome(s): Secondary outcomes include: change in cardiovascular (CV) health as measured by the American Heart Association's Life's Simple 7 (LS7) scores collected via participant survey; change in the nutritional quality of food selected by clients at their food shelf visit as measured by HEI; change in the nutritional quality of food offered at food pantries as measured by HEI during environmental assessments; implementation of policies and practices that promote a nutrition-focused hunger relief network, qualitatively assessed through key informant interviews; and cultural appropriateness of food shelf foods and services as measured by the availability of culturally-specific food, and client satisfaction assessed by pre/post surveys.

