Healthy Eating Index (HEI). For the outcome of change in overall diet HEI scores (the primary outcome), power is computed based on the t-test at the individual client level, but sample size is inflated for the group randomization design by a factor of $1+(m-1)*ICC$ where m is the average cluster size and ICC is the intracluster correlation. A SD of 14.4 is based on change in individual total diet HEI scores from the PI's pilot study of 43 food shelf clients²¹ assuming that individual total diet variability is a better reflection of the variability in client selection than the variability across food

pantries. We anticipate an ICC for HEI scores of 0.05 based on the same data.²¹ Under these assumptions and using a two-sided type I error rate of 5%, this study would have 80% power to detect a mean difference in 7.5 HEI points between intervention and control. With a originally planned average cluster size m of 11 and number of clusters k of 16, we require at least 176 participants with pre/post measures, or at least 272 enrolled to account for 30% attrition. We have surpassed this number for our primary outcome. This calculation also yields more than adequate power to detect the same mean difference in the HEI of food selected at the visit based on actual the standard deviation in our baseline sample (secondary outcome), for which we collected two repeated-sectional samples (with the second sample of 187 collected at post-assessment),.

Enrollment of UConn Students and/or Employees: [Will UConn students be enrolled? If so, describe if these students include those who any key research personnel teaches, or for whom any key research personnel has responsibility. Will UConn employees be enrolled? If so, describe if these employees report to any key personnel. For each group, explain why this population is *necessary* to the study. Tip: convenience is not sufficient justification.]

N/A

Enrollment of Key Personnel, Spouses or Dependents/Relatives: Will study key personnel, spouses of key personnel, or dependents/relatives of any key personnel be enrolled in the study? If so, describe and provide justification.

[figure not shown]
N/A

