Primary outcome (HEI). To examine change in overall diet, we will use mixed-model linear regression models with fixed effects for treatment group, baseline client- and food pantry-level covariates, and a random effect for food pantry (to account for correlation within food pantries) to assess intervention effect on mean change. Change will be calculated as post-intervention score minus pre-intervention score in client-level overall diet HEI score. We will specify a correlation structure for the random effect appropriate for longitudinal data (e.g. autoregressive, Toeplitz or compound

symmetry). Pre and post-intervention component scores and change scores will be calculated for the HEI subcomponents for descriptive purposes. We will also proceed with a sensitivity analysis of the 11 sites where data was collected pre-COVID, as dietary habits may be different during COVID-19, for which we are powered to detect an effect size of 8.15 points.

Secondary and exploratory outcomes. For food selected at the visit, we will compare post intervention HEI scores between intervention and control groups, adjusted for clustering within the food pantry (random effects) and adjusted for food pantry-level baseline HEI bag check scores and relevant covariates (client and food pantry level). HEI subcomponent scores will be calculated for descriptive purposes. We will proceed with analysis of HEI bag check scores for the 11 sites in which we have complete pre/post data, for which we are powered to detect an effect size of 7.27 points. Change in CV health scores (Life's Simple 7) and satisfaction scores will be analyzed using models described above.

Inclusion/Exclusion Criteria: [List ALL inclusion and exclusion criteria. Any proposed exclusion criterion based on gender (women of childbearing potential), age, or race must include justification for the exclusion.]

Inclusion Criteria: Any adult who comes to a participating food pantry on a day in which data collection is taking place will be able to participate in the study, as long as they do not fit our exclusion criteria. This group, based on the demographic of adults who participate in food pantries' services will include groups with socioeconomic disadvantage. Only one adult per household may participate. We will enroll clients who speak English, Spanish or Somali. Participants must have access to a phone.

Exclusion Criteria:

- Under the age of 18
- Mentally incapable of providing informed consent

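### Does asking for a longitudinal correlation structure, when each client has a single change score, put the primary test at risk?

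*Combined protocol and SAP*

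**What the plan says.** Data Analysis Plan, Primary outcome (HEI), defines the outcome by subtraction: "Change will be calculated as post-intervention score minus pre-intervention score in client-level overall diet HEI score". The model has fixed effects for arm and for baseline client and pantry covariates, together with "a random effect for food pantry (to account for correlation within food pantries) to assess intervention effect on mean change". The sentence in question follows: "We will specify a correlation structure for the random effect appropriate for longitudinal data (e.g. autoregressive, Toeplitz or compound" symmetry). No structure is chosen, and no repeated unit or ordering is named.

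Under Secondary and exploratory outcomes, change in Life's Simple 7 "and satisfaction scores will be analyzed using models described above", so the wording carries over to those outcomes.

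Two other places bear on the reading. The Outcomes section gives two measurement occasions: "A cohort of clients will take two 24 hour recalls at each time point to measure overall dietary quality". The Power Analysis inflates the sample by 1 + (m − 1) × ICC and states "We anticipate an ICC for HEI scores of 0.05 based on the same data". That factor treats clients of one pantry as exchangeable.

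**The concern.** A correlation structure for longitudinal data needs repeated measurements in some order. Here each client contributes one number. The two recalls at each occasion feed the score for that occasion, and the two study waves contain different pantries, so neither restores a time axis. The only correlation left is between clients of the same pantry, and they have no natural order.

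The first example listed is autoregressive. If an analyst imposed it on clients in file order, in place of a common pantry effect, the model would treat clients a few rows apart as almost independent. The variance of the arm difference would be understated, the type I error would exceed the two-sided 5% in the Power Analysis, and significance could depend on how the data set was sorted. Because the choice of structure is deferred, the primary model seems open on a point that affects the error rate.

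**Working it through.** **Inputs.** From Power Analysis: SD of change 14.4, difference 7.5, ICC 0.05, m = 11 clients per pantry, k = 16 pantries, two-sided 5%, 80% power. From Design Overview: 8 pantries per arm. From the enrolment section: 214 completers so far, or 214/16 = 13.4 per pantry, so m = 13 is also used. Pantry-level degrees of freedom: 16 − 2 = 14.

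**The plan's own figure.** Per arm, 2 × (1.96 + 0.84)² × 14.4²/7.5² = 57.9, rounded up to 58. The design effect is 1 + 10 × 0.05 = 1.50. Total: 2 × 58 × 1.50 = 174, which becomes 16 × 11 = 176 with whole clusters, at 80.5% power (normal approximation). The stated 176 is reproduced, and it rests on exchangeable clients within a pantry.

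**Autoregressive structure instead of the pantry effect.** With lag-one correlation 0.05, the model's variance factor for a pantry mean is 1 + 2 × Σ(1 − j/m) × 0.05^j, summed over j = 1 to m − 1.

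- m = 11: 1 + 2 × (0.04545 + 0.00205 + 0.00009 + …) = 1.095, against a true 1.50. The variance is understated by 1.50/1.095 = 1.37. A nominal 5% normal test then uses 1.96/√1.37 = 1.67, a true level of about 9.4%.
- m = 13: 1.097 against 1 + 12 × 0.05 = 1.60, a ratio of 1.46 and a level of about 10.5%.

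**Simulated type I error** (true correlation exchangeable, ICC 0.05, equal cluster sizes, no covariates; 10,000 null replicates per setting, 1,500 for Toeplitz). Ranges cover m = 11 and 13.

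| Fitted model | t, 14 df | Normal reference |
|---|---|---|
| Pantry intercept | 3.9–4.5% | 5.9–6.5% |
| Pantry intercept plus AR(1) residual | 4.0–4.5% | 6.0–6.5% |
| Full Toeplitz over clients, m = 11 | 5.2% | 8.0% |
| AR(1) over clients, no pantry effect | 7.3–8.3% | 10.1–11.3% |

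A separate run of 4,000 trials per setting gave 7.3% (m = 11) and 8.5% (m = 13) for the last row on 14 df, and 4.3% and 4.6% for the pantry intercept. AR(1) placed across the pantry effects themselves gave 4.1–5.4% on 14 df.

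**Dependence on the ICC (t, 14 df).** AR(1) without the pantry effect: 4.2–4.7% at ICC 0.01 and 10.2–11.9% at 0.10. Pantry intercept: 2.9–3.3% and 4.5–4.8%.

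**Sort order.** At ICC 0.05, one random re-sort of clients changes significance in 2.1–2.2% of null data sets under AR(1) alone, and in 0.7% when the intercept is kept and AR(1) is added to the residual.

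**What the text permits.** The structure is attached to the random effect, and the random effect is for pantry. A single pantry intercept has a 1 × 1 covariance, so autoregressive, Toeplitz and compound symmetry all give the same fit. Applied among clients of a pantry, compound symmetry is the same model as the intercept for a non-negative ICC, and Toeplitz contains it as a special case. If the authors had pre and post rows in mind, the three structures with common variance coincide at two time points. The autoregressive label does damage only when it displaces the pantry effect.

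**The case for a change.** The best argument for a change is that an analysis plan exists to remove this kind of choice. The unsafe option is the first one listed, the decision is put off, and the wording extends to Life's Simple 7 and satisfaction. A rewrite costs nothing, and some follow-up was still under way, so it could still be specified in advance.

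Part of this stands. The sentence is misplaced, and the arithmetic for the autoregressive-only model is right. Toeplitz over clients is also less comfortable with a normal reference (8.0% against 5.9% for the intercept at m = 11). If pre and post rows were modelled, the pantry effect would have to be carried through to change over time; but that is not the outcome the plan defines.

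What does not stand is the step from loose wording to an inflated test. To get there, an analyst must drop "a random effect for food pantry (to account for correlation within food pantries"), ignore its stated purpose, and invent an ordering of clients that the plan never mentions. The exchangeable design effect in the Power Analysis confirms what was intended. The reference distribution is a separate unstated detail: moving from 14 df to a normal reference takes the plain intercept from 3.9–4.5% to 5.9–6.5% without any help from the longitudinal sentence.

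**Conclusion.** The concern does not call for a change. The sentence about longitudinal structures is a redundant slip in a plan that already states the term that matters. With the pantry random effect kept, type I error on 14 df is about 4% to 5% at ICC 0.05, whichever structure is named. The inflated figures, 7.3–8.3% at ICC 0.05 and up to 11.9% at 0.10, belong to a model that omits that term; at ICC 0.01 even that model holds its level.

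These figures assume equal cluster sizes, no covariate adjustment, and an exchangeable ICC. The plan gives 0.05 for HEI scores without saying explicitly that it applies to change scores, and covariates may lower what remains. None of this affects the conclusion, which rests on the stated pantry effect. Deleting the sentence would make the plan tidier but would leave the fitted model and its results as they are, for the primary outcome and for the secondary outcomes that reuse it.

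### The 8.15-point detectable difference for the 11-site diet analysis is not reached at 80% power on the plan's own SD and ICC once pantry-level degrees of freedom are used, and the 7.27-point cart figure cannot be confirmed

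*Combined protocol and SAP*

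**What the plan says.** The Power Analysis (under Justification of Sample Size) sets out the only documented method: "power is computed based on the t-test at the individual client level", with the sample inflated by 1+(m-1)×ICC. The SD of change is 14.4, the type I error is two-sided 5%, and power is 80% for 7.5 points. On the ICC: "We anticipate an ICC for HEI scores of 0.05 based on the same data". On size: "With a originally planned average cluster size m of 11 and number of clusters k of 16", which gives 176 completers. For carts, the section says "This calculation also yields more than adequate power to detect the same mean difference in the HEI of food selected at the visit", resting on the SD observed at baseline, which is not printed.

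The Data Analysis Plan then gives two figures for 11-site analyses. For diet HEI before COVID-19: "for which we are powered to detect an effect size of 8.15 points". For carts: "for which we are powered to detect an effect size of 7.27 points". Neither figure comes with a sample size, cluster size, arm split or degrees of freedom.

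The diet model includes "a random effect for food pantry (to account for correlation within food pantries". The cart model is also clustered by pantry and is "adjusted for food pantry-level baseline HEI bag check scores and relevant covariates". The Design Overview states that pantries, 8 per arm, are the units randomised. The section on numbers enrolled reports 317 people in Sample A, 214 of them with complete pre/post primary measures across all 16 sites (a few still in follow-up). It also reports 272 baseline carts at 16 sites and 187 post-assessment carts at 11 sites.

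**The concern.** The design effect enlarges the variance for clustering, but the plan's calculation still takes its critical value from a client-level test. Here the treatment contrast is between pantries. With 11 pantries and two arms it has at most 11 − 2 = 9 df, and fewer once pantry-level covariates enter. At 9 df the multiple of the standard error needed for 80% power is about 12% larger than the normal value, so a figure from the client-level method looks better than the planned mixed model can deliver.

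These two numbers are the plan's only statements of what the 11-site analyses can detect, and a null result would be read against them. The diet analysis is the check on whether COVID-19 changed the picture. The 11-site cart analysis is the one the plan will proceed with for food selected.

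**Working it through.** **Inputs.** SD 14.4, ICC 0.05, two-sided 5%, 80% power, m = 11, k = 16 (Power Analysis); 214 completers at 16 sites, 187 carts at 11 sites (numbers enrolled). Assumed: equal arms, no covariate gain, and 80% power carried over to the 11-site figures. The last is the natural reading, since by the plan's formula 8.15 at 90% power would need about 309 completers.

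**Formulae.** DE = 1 + (m − 1)×ICC with m = N/11; SE = SD×√(4×DE/N); detectable difference = multiplier × SE. The multiplier is 2.802 (normal) or 3.150 (noncentral t, 9 df); ratio 1.124.

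**Step 1: the plan's main figure.** N = 176, DE = 1 + 10×0.05 = 1.5, SE = 14.4×√(6/176) = 2.659. The detectable difference is 2.659×2.802 = 7.45 (normal), or 7.51 with the client-level t. The stated 7.5 reproduces.

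**Step 2: where 8.15 could come from.** With DE matched to the site size, the client-level method gives 8.15 at about 168 completers (normal) or 174 (t). With DE left at the planned 1.5, it gives 8.15 at 147 (normal: 14.4×√(6/147)×2.802 = 8.15) or 150 (t). The pro-rata share of completers is 214×11/16 ≈ 147, or 13.4 per site; its own DE is 1.618, and the plan's formula then gives 8.46 or 8.47, depending on rounding. Which route was used cannot be determined.

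**Step 3: diet with 9 df.**

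| Completers at 11 sites | DE | SE | Client-level (normal) | 9 df | Power at 8.15, 9 df |
|---|---|---|---|---|---|
| 147 (pro rata, assumed) | 1.618 | 3.022 | 8.47 | 9.52 | 67% |
| 168 | 1.714 | 2.909 | 8.15 | 9.16 | 70% |
| 214 (all completers) | 1.923 | 2.730 | 7.65 | 8.60 | 76% |

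Solving 3.150 × SE = 8.15 gives N ≈ 269, more than the 214 completers reported at all 16 sites. Eleven sites cannot split equally; 6:5 gives 9.56, 9.20 and 8.63. With 8 df (one pantry-level covariate) and equal arms, the values are 9.67, 9.31 and 8.74.

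**Step 4: dependence on the ICC** (9 df, equal arms). Completers needed for 8.15:

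| ICC | N needed |
|---|---|
| 0.02 | about 157 |
| 0.03 | about 181 |
| 0.04 | about 216 |
| 0.05 | about 269 |

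Above 0.05 it is further out of reach: at ICC 0.10 and N = 214 the detectable difference is about 10.5.

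**Step 5: carts.** With 187 carts, SD 14.4 and DE 1.5, the client-level t gives 7.28, close to the stated 7.27. But 187/11 = 17 carts per site, so at ICC 0.05 DE = 1 + 16×0.05 = 1.8 and SE = 14.4×√(7.2/187) = 2.826. That gives 7.92 by the plan's formula (normal) and 8.90 with 9 df. The SD of 14.4 is the diet value, used here only because the cart SD is not printed.

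**The case against.** The strongest reply on diet is that nothing is miscalculated. The Power Analysis states the method, SD, ICC, error rate and power, and by that method about 168 to 174 completers give 8.15, which is below 214. This stands. A reader might infer an arithmetic slip, or that the design effect was certainly left at its planned value. The documents support neither: the weakness is the df basis, and the route to 8.15 is only a back-solution.

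Second, the ICC of 0.05 is an anticipated value from a 43-client pilot. This also stands. At 0.02 or 0.03 the figure is within reach of 214 completers, so the shortfall is conditional on the plan's own ICC.

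Third, the planned covariates could recover precision. They could: restoring 8.15 with 9 df needs the variance of the treatment contrast cut by 27%, 21% or 10% at 147, 168 or 214 completers. The plan claims no such gain and gives no basis for one. Likewise 147 is only a pro-rata assumption; if those still in follow-up are mostly at the later sites, the 11 sites hold a larger share of the 214. The conclusion does not need 147, since it holds even at 214.

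On carts, a reader might infer that 7.27 is wrong, or scale it up by 12% and quote a loss of power at 7.5 points. Neither is supported. The plan says the observed SD was used, so the match with SD 14.4 and the planned design effect may be coincidence. Scaling 7.27 would also take for granted that it already reflects 17 carts per site.

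**Conclusion.** The diet point holds, conditionally. On the plan's SD of 14.4 and ICC of 0.05, with equal arms, no covariate gain and 9 df, 8.15 points is not attained at 80% power for any number of completers up to 214. The detectable difference is 8.6 to 9.5 points over 214 down to 147 completers. The chance of missing a true 8.15-point effect is 24% to 33% instead of 20%. An ICC of about 0.03 or lower, or a supported covariate gain, could remove the shortfall.

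The cart figure of 7.27 can be neither confirmed nor refuted. Its agreement with the planned design effect suggests, without proving it, that m = 11 was kept although there are 17 carts per site.

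Severity is minor. The affected items are a sensitivity analysis and a secondary outcome, and enrolment is closed. A reader might infer that the main result is compromised, but these figures play no part in the primary test or estimate.

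**What to change.** Recompute both 11-site detectable differences with pantry-level df, the actual completers or carts per site, and the actual arm split. For carts, use the observed baseline SD and an ICC estimated from the 272 baseline carts. Beside each figure state N, m, arm split, SD, ICC, power, df and any assumed covariate gain with its basis, and show a short ICC range. Replace 8.15 and 7.27 with the results, and keep the Power Analysis statement that cart power is more than sufficient only if the recomputed figure supports it. The values worked out here show the size of the issue and are not meant for the plan.

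The cost is a recalculation from data in hand and a few lines of text; no new data are needed. The downside is that the stated figures will probably become less favourable.
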